6.5 Pharmacokinetics

6.5.1 Blood Collection for PK Analysis

In Part A, intensive blood samples will be collected from all subjects for evaluation of PK of CC-90009 in plasma at time points specified in Table 40, Table 41, Table 42, or Table 43. In Part B, intensive blood samples will be collected from approximately 10 selected subjects in each cohort for evaluation of PK of both CC-90009 and hydroxypropyl- β -cyclodextrin in plasma; sparse blood samples will be collected from the remaining subjects for evaluation of PK of CC-90009. Time points are specified for intensive and sparse PK sampling, respectively in Table 44 or Table 8.

The concentration of R- and S-enantiomers of CC-90009, ie CC0782618 (R-enantiomer) and CC0782619 (S-enantiomer), in plasma will be determined by LC/MS. The CC-90009 concentration will be calculated as a sum of its R- and S-enantiomers. An exploratory analysis of CC-90009 metabolites in plasma may be performed utilizing the blood samples collected for PK evaluation.

The blood PK samples at 2, 15, and 30 minutes after the EOI MUST be collected from the arm contralateral to the arm used for CC-90009 administration. If a peripheral IV catheter is used for the CC-90009 IV administration, the PK samples should be obtained from the opposite arm. In general, blood for PK samples should not be drawn from a central line. If a peripheral line is not accessible, blood for PK samples drawn from a central line MUST be collected after the lumen is flushed with saline, and the non-dosing lumen of a dual/triple lumen catheter should be used. Administration and PK blood draw locations will be recorded in the database.

Table 8:	Blood Pharmacokinetic Sampling Schedule in Part B: 2.4 and 3.0
	mg Days 1-7 Schedule

Time Relative to CC-90009 Administration	Collection Window	Intensive	Sparse
Cycle 1 Day 1 and Cyc	ele 1 Last Dose		
0	\leq 30 minutes prior to start	Х	
Mid-infusion (eg, at 15 minutes in a 30 minute infusion) ^a	± 1 minute	Х	
15 minutes after EOI	± 5 minutes	Х	
30 minutes after EOI	± 5 minutes	Х	Х
1 hour after EOI	± 5 minutes	Х	Х
2 hours after EOI	± 10 minutes	Х	
4 hours after EOI	± 10 minutes	Х	Х
8 hours after EOI	\pm 30 minutes	Х	
12 hours after EOI	± 2 hours	Х	
24 hours after EOI	\pm 3 hours	X ^b	Xb
Cycles 2-			
Second to last dosing day, pre-dose	\leq 30 minutes prior to start	Х	Х
Last dosing day, pre-dose	\leq 30 minutes prior to start	Х	Х

Abbreviation: EOI = end of infusion/injection.

^a In cases where the only access for drug administration is the central line, mid-infusion PK draws may be omitted.

^b 24 hours after EOI on day 1 occurs on Day 2. Must be drawn prior to the administration of CC-90009 on Day 2.

The following information must be captured in the eCRFs:

- The dose level and total dose administered.
- The actual clock time of the start of the CC-90009 IV administration.
- The actual clock time of the EOI.
- The actual clock time of each PK sample collection.
- The location of drug administration and PK sample collection.

The Sponsor may conduct additional analyses on the PK samples in order to follow-up the safety of the study treatment or to better understand the progression of the disease or the disease's response to the study treatment.

See the Laboratory Manual for sample collection, handling, and processing instructions.

6.5.2 Urine Collection for PK Analysis

Urine will be collected in approximately 10 evaluable subjects in Part A and/or Part B. Collection will occur on Cycle 1 Day 1. Urine will be collected predose (within approximately 60 minutes prior to dosing; spot collection to serve as the blank control) and then pooled as a single block over the intervals of 0 to 4, 4 to 8, 8 to 12, and 12 to 24 hours postdose. Within approximately 15 minutes of ending each collection interval, subjects should empty their bladder prior to the start of each new collection interval. This urine should be added to the pooled urine for the current collection interval. During each collection interval, all urine voided must be collected (ie, no urine should be allowed to pass into the toilet). Incomplete collection or missed samples will be recorded as a deviation.

The concentration of CC-90009 and hydroxypropyl- β -cyclodextrin in urine will be determined. An exploratory analysis of CC-90009 metabolites in urine may be performed utilizing the urine samples collected for PK evaluation.

The following information must be captured in the eCRFs:

- The dose level and total dose administered.
- The actual clock time of the start and end of the CC-90009 IV administration.
- The actual clock time of the start and end of each urine collection interval.
- The weight of urine collected during each collection interval (eg, 200 g during the 0 to 4 hours postdose collection interval).

See the Laboratory Manual for sample collection, handling, and processing instructions.

6.6 Biomarkers, Pharmacodynamics, Pharmacogenomics

6.6.1 Pharmacogenomics Sample

A sample (eg, buccal swab or nail clippings) will be collected prior to dosing on Cycle 1 Day 1 for assessment of potential pharmacogenomics markers of CC-90009 safety, activity or exposure.

6.6.2 Pharmacodynamic Biomarker Blood Samples

The schedules for blood collections for pharmacodynamic biomarkers are provided in Table 9 and Table 10.

Table 9:Sample Collection of Blood for Pharmacodynamic Biomarkers on D1-5Schedule and Alternative Schedules with up to 10 consecutive dosing
days (eg, D1-7 and D1-10) for Part A or Part B

			Cycle 1 ^a									
	Screeni ng	D	ay 1	Day	Day 2		Day 3		Last Day of Dosing	Day 8 ^b	Day 15	Day 28 ^d
Sample	Day - 14 to -1°	Pred ose (≤ 3 hrs)	6 hours (± 15 min) after EOI	Predose (≤ 3 hrs)	6 hours (± 15 min) after EOI	Predose (≤ 3 hrs)	6 hours (± 15 min) after EOI	Predose (≤ 3 hrs)	6 hours (± 2 hr) after EOI	AM	AM	AM
Whole blood, flow cytometry ^a	Х	Х	Х	X ^g	Xg	X	Х			Х	Xg	Х
Whole blood, PD biomarkers	X ^d								X ^{d,e}			X ^{d,e}
Blood for PBMC, PD protein & RNA ^a	Х	Х		X ^g		Х				Х		
Blood for PBMCs, ex vivo sensitivity assays, phenotyping & sequencing		Х										
Blood for plasma, cytokine assays	X	Х		Х		Х		Х		Х		
SARS-CoV-2 Serology ^f		Х										

Abbreviations: AM = morning; EOI = end of infusion/injection; PBMC = peripheral blood mononuclear cells; PD = pharmacodynamic; RNA = ribonucleic acid; SARS-CoV-2 = severe acute respiratory syndrome coronavirus 2.

- ^a If intra-subject dose escalation occurs, blood samples for PD assays will also be collected during the first cycle at the increased dose on Days 1, 2, 3, 4, 8 and 15; see laboratory manual for details.
- ^b If Day 8 is a dosing day due to use of an alternate schedule per the SRC, obtain samples pre-dose.
- ^c Obtaining the Screening samples on the same day as the Screening bone marrow aspirate and biopsy is preferred.
- ^d For subjects in Part B only. Last day of dosing is defined as the last consecutive planned day (eg, Day 5 on the Days 1-5 schedule or Day 7 of the Days 1-7 schedule). See also footnote e and Section 6.6.3 for allowable days for the Cycle 1 Last Day of Dosing sample collection (ie, on Days 1-5 schedule, Day 4 or 5; on Days 1-7 schedule, Day 6, 7, or 8).

^e Collected the same day the bone marrow samples are collected for PD or response assessments in Cycles 1, 2 and 4

^f Serum collected to be used for possible measurements of anti-SARS-CoV-2 serology (anti-SARS-CoV-2 total or IgG (see Table 6)

^g For Part A only.

		Cycle 1											
	Screening	D	ay 1	Day 2	Day 3	Day 4	Day 8	Day 9	Day 15	Day 22			
Sample	Day -14 to -1 ^a	Predose (≤ 3 hrs)	6 hours (± 15 min) after EOI	Predose (≤ 3 hrs)	Predose (≤ 3 hrs)	AM	Predose (≤3 hrs)	Predose (≤3 hrs)	AM	AM			
Whole blood, cytometrya	Х	Х	х	х	Х		Х	Х	Х	Х			
Blood for PBMC, PD protein & RNA ^a	Х	х		Х		Х	х	х					
Blood for PBMCs, ex vivo sensitivity assays, phenotyping & sequencing		Х											
Blood for plasma, cytokine assays	Х	Х		Х	Х	Х	Х	Х	Х				

Table 10:Sample Collection of Blood for Pharmacodynamic Biomarkers using
the Alternate D1-3/D8-10 Schedule for Part A or Part B

Abbreviations: EOI = end of infusion/injection; PD = pharmacodynamic; RNA = ribonucleic acid.

^a Obtaining the Screening samples on the same day as the Screening bone marrow aspirate and biopsy is preferred.

6.6.3 Pharmacodynamic Biomarker Bone Marrow Samples

Bone marrow aspirates and biopsy for PD and prognostic/predictive biomarkers will be collected at the time points indicated in Table 4 – Table 7, Appendix K, or Appendices M-O. Exploratory tests may be performed to determine Minimal Residual Disease (MRD) status at efficacy time points. In Cycle 1 on Day 5 on the D1-5 dosing schedule, the PD samples will be collected between 4 to 8 hours after CC-90009 is administered. If necessary due to scheduling conflicts, the PD samples may be collected on Day 4 (4 to 8 hours after dosing). If the dosing interval (schedule) is extended, then samples will be obtained on the last day \pm 1 day (ie, if extended to consecutive 7 days or 10 days, the PD bone marrow sample can be collected on Day 6-8 [Appendix M] or 9-11 [Appendix O]). For the D1-3/D8-10 schedule, the PD bone marrow sample is collected on Day 9 or 10 (Appendix K).

Additionally, bone marrow aspirates and/or biopsies may be obtained in both Part A and Part B, after a CR is confirmed, if relapse is suspected, or following treatment discontinuation to elucidate effects of long-term treatment or resistance mechanisms, or as clinically indicated based on the Investigator's medical assessment. When obtained for any of the reasons above, samples for biomarker assessments will also be collected at the same time.

6.6.4 SARS-CoV-2 Serology Samples

Serum and plasma samples may be assessed by enzyme-linked immunosorbent assay, seromics, ctDNA measurements, metabolomics, and/or other relevant multiplex-based protein assay methods for immune-related factors that may be associated with efficacy or AEs; such factors may include, but are not limited to, assessments of cytokines, chemokines, inflammatory factors, SARS-CoV-2 serologic status, and ctDNA. Serum will be collected predose on Cycle 1 Day 1 (or at screening), approximately every 6 months during study treatment and at EOT to be used for possible measurements of anti-SARS-CoV-2 serology (anti-SARS-CoV-2 total or IgG). Serum should also be collected approximately 4 weeks after documented or suspected SARS-CoV-2 infection (see Table 6 – Table 7 and Table 35 – Table 36).

6.6.5 All Pharmacodynamic and Pharmacogenomics Samples

Refer to the Laboratory Manual for sample collection, handling, and processing instructions.

The Sponsor may conduct additional analyses on the biomarker samples in order to follow up the safety of the study treatment or to better understand the progression of the disease or the disease's response to the study treatment or the subject's predisposition to therapeutic response to CC-90009.

6.7 Additional and Optional Research

Additional and optional research as described below may be performed using left-over samples originally collected for another test required in this study or using samples collected specifically for biomarker testing. The research may involve genetic tests using DNA or RNA and may lead to the development of new diagnostic tests.

6.7.1 Additional Research

Additional research related to the study drug and/or disease may be performed. The results of this additional research could help to improve the diagnosis and/or the treatment of this disease in the future.

6.7.2 Optional Research

Optional research not related to the study drug or the subject's disease may be performed. The subject's decision to participate in this optional research will not impact their ability to participate in the main study.

6.8 Subject Reported Outcomes

Not Applicable

7 DESCRIPTION OF STUDY TREATMENT

7.1 Description of Investigational Product

7.1.1 Physical Properties

CC-90009 has a molecular weight of 461.85 g/mole. It is a white to off-white powder.

7.1.2 Formulation

Celgene Corporation will supply CC-90009 clinical drug product as a lyophilized powder for reconstitution to solution in single-use vials and it should be stored per the product label. The drug product is available in two different formulations: Gen 1 and Gen 2b. The study will initially employ Gen 1 (DL1: 0.3 mg, DL2: 0.6 mg, and DL3: 1.2 mg), and then during dose escalation, Gen 2b was introduced at DL4 (2.4 mg) to replace the Gen 1 formulation. Each vial of Gen 1 CC-90009 contains 1.05 mg of CC-90009, 18.6 mg anhydrous citric acid, 18.5 mg anhydrous sodium citrate, and 252.0 mg of Kleptose[™] hydroxypropyl beta-cyclodextrin (HPBCD) as a freeze dried powder. CC-90009 is slightly hygroscopic. Each vial of Gen 2b formulation of CC-90009 contains 1 mg CC-90009 and 800 mg hydroxypropyl-beta-cyclodextrin (HPBCD) as a freeze dried powder. CC-90009 clinical drug product is packaged in a 20 mL US Pharmacopeia (USP) Type I glass vial or local equivalent. The CC-90009 vial does not contain any preservative and is for single use only. CC-90009 should be prepared according to the package instructions, the CC-90009 Pharmacy Manuals, and local practice regulations. Gen 1 formulation is reconstituted in sterile Water for Injection (SWFI). Gen 2b formulation is reconstituted in 0.45% sodium chloride (half strength normal saline) and further diluted in 0.9% sodium chloride (normal saline) for injection (eg, for infusion doses between 0.6 and 10 mg, Gen2b formation is reconstituted with 4.5 mL of 0.45% sodium chloride [half strength normal saline] to a concentration of 0.2 mg/mL The reconstituted solution can be further diluted in 0.9% sodium chloride [normal saline] to achieve a 50 mL volume.)

DMA is a process solvent used during manufacture of Gen 1 formulation of CC-90009 that is removed during processing. The daily dose of DMA residual solvent in Gen 1 CC-90009 must not exceed the ICH permitted daily exposure limit (10.9 mg/day) to proceed with dose escalation above a CC-90009 daily dose of 2.4 mg. Gen 2b CC-90009 was developed to enable doses above the limits imposed on Gen 1 formulation. Gen 2b CC-90009 is permitted at doses up to 20 mg CC-90009 per day. The SRC determined the dose cohort for introduction of Gen 2b CC-90009 during Part A of the study to be DL4: 2.4 mg on Days 1-5.

Females of childbearing potential and fertile males should not handle or administer CC-90009 unless they are wearing gloves.

7.2 Treatment Administration and Schedule

CC-90009 will be administered QD on Days 1 to 5 (on the D1-5 dosing schedule) of Cycles 1 to 4. Subjects will be closely monitored throughout the administration of CC-90009 and for 1 hour following each administration. In addition, subjects will be admitted as inpatients for each administration of CC-90009 and monitoring in Cycle 1. For Cycles ≥ 2 , subjects will either be admitted as inpatients or treated/monitored in a LSU per Investigator's discretion. Subjects with

Grade ≥ 2 hypocalcemia in any cycle should be treated as inpatients in subsequent cycles (an exception can be made for subjects with grade 2 hypocalcemia lasting less than 24 hours that recovers without IV calcium [eg, calcium gluconate or calcium chloride] after discussion with the Celgene medical monitor). The SRC may evaluate modified dosing schedules (eg, increasing from 5 to up to 10 consecutive days of dosing, intermittent schedules or longer infusion times) in additional cohorts, if necessary, based on toxicity, PK profiles, and PD findings.

For CC-90009 doses at or above 3.6 mg, all subjects will receive a dose of steroids (eg, dexamethasone 10 mg IV (or by mouth [PO] or equivalent) 30 min to 3 hrs prior to each daily dose of CC-90009 (Table 4 –Table 7, Appendix K, or Appendices M-O). For CC-90009 dosed at 3.0 mg on the Days 1-7 and Days 1-10 dosing schedules, steroid premedication is recommended for each of the dosing days. On these schedules with longer dosing days, a lower dose of dexamethasone may be given (minimum of 4 mg) per Investigator's judgement based on the subject's expected tolerability of corticosteroids. The frequency and/or the dose of dexamethasone (or equivalent) administration may be modified based on evaluation and recommendation by the SRC (eg, D1-5, D1-7, D1-10, or D1, D3, D5).

All subjects will be required to start calcium, calcitriol, and vitamin D supplementation at least 3 days prior to the first dose of CC-90009 in each cycle and continue until \geq 3 days after the last dose of CC-90009 in each cycle (eg, \geq Day 8 when CC-90009 is administered on Days 1-5, \geq Day 10 when CC-90009 is administered on Days 1-7, or \geq Day 13 when CC-90009 is administered on Days 1-3/8-10 or Days 1-10). Supplementation may be extended if hypocalcemia occurs (refer to Section 7.2.13.2). The time and date of administration will be recorded on a diary card.

The calcium/calcitriol/vitamin D supplementation regimen is:

- Calcium carbonate 500 mg elemental calcium PO 3 times a day (TID) (taken after meals to increase absorption)
 - Alternative preparations of calcium can be substituted but they must equal at least 1200 mg of elemental calcium per day given in divided doses (eg, TID).
 - If the subject is on a proton pump inhibitor (PPI) or has gastric achlorhydria, then administer calcium citrate 630 mg elemental calcium PO TID
- Calcitriol 0.25 micrograms PO QD
- Vitamin D supplementation is based on the Screening serum 25-hydroxyvitamin D level:
 - Level < 12 ng/mL excluded from the study
 - Level 12 20 ng/mL Vitamin D3 or D2 50,000 IU weekly
 - Level > 20 ng/mL- Vitamin D3 or D2 1000 IU QD

The risk of TLS with CC-90009 is unknown. Subjects should be adequately hydrated (eg, 2 to 3 liters of oral or IV fluids per day) starting the day prior to CC-90009 administration and continuing through each day of CC-90009 administration. Medications to prevent or treat TLS are permitted (refer to Section 8.1).

In the absence of progressive disease (as defined in Section 6.4) or unacceptable toxicity, subjects may continue treatment with CC-90009 for a maximum of 4 cycles if they are deriving benefit, as judged by the Investigator.

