In the Treatment Period, CC-90009 will be administered intravenously on Days 1-5 of each 28 day cycle for up to 4 cycles in the absence of disease progression (as defined in Section 6.4), relapse, unacceptable toxicity, or subject/physician decision to withdraw. Modified dosing schedules (eg, increasing from 5 consecutive days to up to 7 or 10 consecutive days of dosing or increasing infusion length) may be evaluated in additional cohorts, if necessary, based on toxicity, PK profiles, and PD findings. An additional schedule of CC-90009 administered once daily on Days 1-3 and Days 8-10 of each 28-day cycle will be explored. Those who demonstrate benefit from treatment without unacceptable toxicity (any complete remission [CR], morphologic leukemia-free state [MLFS], partial remission [PR], or stable disease with discussion with Medical Monitor) may continue treatment beyond Cycle 4 until loss of that benefit, unacceptable toxicity, or subject/physician decision to withdraw.

All subjects will be required to start calcium, calcitriol, and vitamin D supplementation at least 3 days prior to Day 1 of each cycle and continue until \geq 3 days after the last dose of CC-90009 in each cycle (eg, \geq Day 8 when CC-90009 is administered on Days 1-5, \geq Day 10 when CC-90009 is administered on Days 1-7, or \geq Day 13 when CC-90009 is administered on Days 1-10 or Days 1-3/Days 8-10).

In Cycle 1 of Part A, a bone marrow evaluation will be performed on Day 28 (\pm 3 days). Based on the Day 28 bone marrow evaluation, subjects with hypoplastic bone marrow, without evidence of persistent leukemia, who have Grade \geq 3 neutropenia will be followed for an additional 2 weeks for safety monitoring in Cycle 1 (total duration of 42 days; refer to Figure 1). An additional bone marrow assessment will be performed at the time of hematologic recovery or Day 42 (\pm 3 days). Thus, in Part A, the window for evaluation of dose-limiting toxicity (DLT) during Cycle 1 will be up to 42 days (28 or 42 days). In Part B, Cycle 1 will be 28 days in length. Cycles \geq 2 will be 28 days in length. Subsequent cycles should start \leq 7 days following the last day of the previous cycle. Permitted treatment delays are described in Section 7.2.12.

Follow-up Period

In the Follow-up Period, all subjects will be followed for 28 days (\pm 3 days) after the last dose of CC-90009 for safety.

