In the Treatment Period, CC-90009 will be administered intravenously QD on Days 1-5 of each cycle for up to 4 cycles in the absence of disease progression (as defined in Section 6.4), relapse, unacceptable toxicity, or subject/physician decision to withdraw. Modified dosing schedules (eg, increasing from 5 consecutive days to up to 7 or 10 consecutive days of dosing or increasing infusion length) may be evaluated in additional cohorts, if necessary, based on toxicity, PK profiles, and PD findings. An additional schedule of CC-90009 administered once daily on Days 1-3 and Days 8-10 of each 28 day cycle will be explored. Tables of Events for the alternate dosing schedules (eg, D1-3/D8-10, D1-7, and D1-10 Dosing Schedules) are located in Appendix K and Appendices M-O. Those who demonstrate benefit from treatment without unacceptable toxicity (any complete remission [CR], morphologic leukemia-free state [MLFS], partial remission [PR], or stable disease with discussion with Medical Monitor) may continue treatment beyond Cycle 4 until loss of that benefit, unacceptable toxicity, or subject/physician decision to withdraw.

All subjects will be required to start calcium, calcitriol, and vitamin D supplementation at least 3 days prior to Day 1 of each cycle and continue until \geq 3 days after the last dose of CC-90009 in each cycle (eg, \geq Day 8 when CC-90009 is administered on Days 1-5, \geq Day 10 when CC-90009 is administered on Days 1-7, or \geq Day 13 when CC-90009 is administered on Days 1-3/Days 8-10 or Days 1-10).

In Cycle 1 of Part A, a bone marrow evaluation will be performed on Days 28 (\pm 3 days). Based on the Day 28 bone marrow evaluation, subjects with hypoplastic bone marrow, without evidence of persistent leukemia, who have Grade \geq 3 neutropenia will be followed for an additional 2 weeks for safety monitoring in Cycle 1 (total duration of 42 days; refer to Figure 1). An additional bone marrow assessment will be performed at the time of hematologic recovery or Day 42 (\pm 3 days). Thus, in Part A, the window for evaluation of DLT during Cycle 1 will be up to 42 days (28 or 42 days). In Part B, Cycle 1 will be 28 days in length. Cycles \geq 2 will be 28 days in length. Subsequent cycles should start \leq 7 days following the last day of the previous cycle. Permitted treatment delays are described in Section 7.2.12.

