pooled in each cohort by dose level for analysis of safety, PK, and PD, which will include between 6 and 40 subjects with up to 20 subjects with R/R AML and up to 20 subjects with R/R HR-MDS in each cohort. The cohorts will enroll subjects in parallel. Up to 6 subjects per cohort will be initially enrolled as a safety run-in. The SRC will assess tolerability of the dose and schedule for these initial subjects that completed at least one cycle of study treatment based on the Part A stopping criteria (Section 7.2.8) and recommend further expansion of one or more cohorts. The expanded cohort(s) will be monitored for the excess toxicities including sepsis utilizing the non-binding Bayesian stopping criterion on a continuous basis (Section 9.9.3). The SRC will continue to review safety and preliminary efficacy data regularly throughout the study and make recommendations about study continuation, cohort continuation, and dose modification, as appropriate.

The study will be conducted in compliance with International Council for Harmonisation (ICH) of Technical Requirements for Pharmaceuticals for Human Use/Good Clinical Practice (GCP) and applicable regulatory requirements.

Figure 1: Study Schema for Dose-Limiting Toxicity Window in Part A (Dose Escalation)

DLT = dose-limiting toxicity.

^a Modified dosing schedules (eg, increasing from 5 to 10 days) may be evaluated in additional cohorts, if necessary, based on the review by the Safety Review Committee of available safety and laboratory data, PK profiles, and PD findings.

[figure not shown]
^b Progressive disease is defined in Section 6.4.

^c In the absence of progressive disease (or relapse) or unacceptable toxicity, subjects may continue treatment with CC-90009 through Cycle 4 if they are deriving benefit, as judged by the Investigator (refer to Section 6.4). Additional cycles of treatment beyond Cycle 4 may be allowed after discussion with the Medical Monitor if the subject is demonstrating clinical benefit (stable disease or PR) and tolerating the study drug without unacceptable toxicity.

^d Additional bone marrow assessment performed at the time of hematologic recovery or Day 42 (refer to Table 4, Table 31, Table 33, or Table 37).

^e Eligible subjects proceed to Cycle 2.

Figure 2: Sample Dose Escalation Schemes for Part A with an NTD of 8.1 mg Example 1

[figure not shown]
Example 2

Escalations proceed by 100% increments with \geq 1 subject cohorts until:

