Treatment failure will be defined as progressive disease or not achieving at least partial remission (PR) by the end of the treatment period. In the absence of progressive disease (as defined above) or unacceptable toxicity, subjects may continue treatment with CC-90009 through Cycle 4 if they are deriving benefit, as judged by the Investigator. Failure to achieve a response and not meeting the criteria for progressive disease will be considered stable disease. Additional cycles of treatment beyond Cycle 4 may be allowed after discussion with the Medical Monitor if the subject is demonstrating clinical benefit (stable disease or PR or CR) and if tolerating the study drug without unacceptable toxicity.

Bone marrow aspirates and biopsies are to be evaluated for morphology, flow cytometry, karyotype, and molecular studies (eg, *FLT3, KIT, NPM1, CEBPa* mutational status if positive on previous bone marrow biopsies). In Part B, bone marrow analyses will be performed at a central laboratory. Molecular and cytogenetic studies may be omitted at the:

- Screening bone marrow evaluation, if they were completed within the prior 90 days and the results are available to enter on the eCRFs,
- Part A, Cycle 1 Day 42 ± 3 days (or at time of hematologic recovery) bone marrow evaluation for subjects with extended safety monitoring in Cycle 1 if a complete response is documented on Day 28.

The marrow aspiration and core sampling (biopsy) should be performed according to the standard of care and analyzed at the local site's laboratory in accordance with the International Council for Standardization in Hematology (ICSH) Guidelines (Lee, 2008).

The clinical activity of CC-90009 will be evaluated by the Investigator by assessing response to treatment according to the IWG Response Criteria in AML (Cheson, 2003; refer to Appendix C).

Treatment decisions will be based on Investigator's assessment. MDS response will be based on the IWG Response Criteria for Myelodysplasia (Cheson, 2006; refer to Appendix G).

Subjects who discontinue treatment for reasons other than disease progression (or relapse), start of a new anticancer therapy, or withdrawal of consent from the entire study will have disease assessments performed up to a maximum of 2 years according to the specified assessment schedule (refer to Section 6.3.2) until progression and/or initiation of new systemic anticancer therapies.

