CC-90009-related AE/SAE follow-up							Re	fer to Sect	tion 6.3.1					
Anticancer therapies	Refer to Section 6.3.2													
Survival	Refer to Section 6.3.3													
Transformation to AML for MDS	After signing ICF and until death, lost to follow-up, withdrawal of consent for further data co											llection, or o	end of trial.	

Abbreviations: Adverse event = AE; AML = acute myeloid leukemia; β -CTx = beta C-terminal telopeptide; C = cycle; Ca = calcium; CD = cluster of differentiation; D = day; ECHO = echocardiogram; ECG = electrocardiogram; ECOG PS = Eastern Cooperative Oncology Group performance status; EOT = End of Treatment; FCBP = females of child bearing potential; INR = international normalized ratio; IV = intravenous; LVEF = left ventricular ejection fraction; MDS = myelodysplastic syndromes; Mg = magnesium; MUGA = multi-gated acquisition scan; P1NP = procollagen type 1 N-terminal propeptide; PD = pharmacodynamic; PK = pharmacokinetic; PPP = pregnancy prevention plan; PT = prothrombin time; PTH = parathyroid hormone; PTT = partial thromboplastin time; q = every; SAE = serious adverse event; TSH = thyroid-stimulating hormone; WK = week.

- ^a All study visits/procedures will have a ± 2 day window and all laboratory blood samples should be drawn predose (≤ 5 hrs), unless otherwise specified in this table or Section 6. Cycles should start ≤ 7 days after the last day of the previous cycle.
- ^b EOT Visit performed within 28 days after last dose of CC-90009 for subjects that discontinue prior to completing dosing in Cycle 4. For subjects that complete dosing in Cycle 4, this visit should be completed on Day 28 (± 2 days) of Cycle 4. For subjects who complete dosing after Cycle 4, EOT Visit should be completed within 28 days after the last day of the previous cycle.
- ^c Safety Follow-up Visit is performed 28 days (± 3 days) after the last dose of CC-90009 for all subjects. May be performed by telephone contact if pregnancy testing is not required (refer to footnote "i").
- ^d Supplements to be administered for at least 3 days after the last dose in each cycle. Supplementation may be prolonged if hypocalcemia occurs (refer to Section 7.2.13.2). Subjects to start supplements at least 3 days prior to Day 1 of Cycles 3 and 4 as per Section 7.2.

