- ⁿ For subjects that complete dosing in Cycle 4, performed/obtained once on Day 28 (± 3 days). For subjects that continue (after consultation with Medical Monitor) beyond Cycle 4, efficacy and bone marrow PD assessments may be obtained to confirm a CR, if relapse is suspected, or following treatment discontinuation to elucidate effects of long-term treatment or resistance mechanisms. Additional aspirates and biopsies will be collected as clinically indicated based on the Investigator's medical assessment. Refer to Section 6.3.2 and Section 6.4.
- ^o Predose blood sample for both intensive and sparse sampling schedule in Cycles 2-4. Refer to Sections 6.5 and 6.6.
- P Serum will be collected approximately every 6 months during study treatment and at EOT to be used for possible measurements of anti-SARS-CoV-2 serology (anti-SARS-CoV-2 total or IgG). Serum should also be collected approximately 4 weeks after a documented or suspected SARS-CoV-2 infection.

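### Section 7.2 caps benefiting subjects at four cycles, while the rest of the protocol lets them continue beyond Cycle 4

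*Combined protocol and SAP*

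**What the plan says.** Section 7.2 opens by describing dosing on the Days 1-5 schedule in Cycles 1 to 4. It closes by saying that subjects without progressive disease or unacceptable toxicity "may continue treatment with CC-90009 for a maximum of 4 cycles if they are deriving benefit", as judged by the Investigator. It cites Section 6.4 in that closing sentence, but only for the definition of progression.

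Other parts of the protocol allow more:

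- **Protocol Summary and Section 3.1 (Treatment Period).** The base course is up to four cycles. Subjects with benefit ("any complete remission [CR], morphologic leukemia-free state [MLFS], partial remission [PR], or stable disease with discussion with Medical Monitor") then "may continue treatment beyond Cycle 4 until loss of that benefit, unacceptable toxicity, or subject/physician decision to withdraw".
- **Section 6.4.** Treatment runs through Cycle 4, and further cycles may be given "after discussion with the Medical Monitor if the subject is demonstrating clinical benefit (stable disease or PR or CR") and is tolerating the drug.
- **Section 3.1, Figure 1 footnote c (Part A).** "Additional cycles of treatment beyond Cycle 4 may be allowed after discussion with the Medical Monitor"; the benefit it names is stable disease or PR.
- **Table 36 (Part B, Days 1-7) and Table 7 (Part B, Days 1-5).** Footnote b states: "For subjects who complete dosing after Cycle 4, EOT Visit should be completed within 28 days after the last day of the previous cycle". Footnote n begins: "For subjects that continue (after consultation with Medical Monitor) beyond Cycle 4". The serology row in each table gives Day 1 of Cycles 6 and 12 as examples of on-treatment collection.

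**The concern.** Section 5 sends sites to Section 7 for details of administration, so 7.2 is where a site would look to learn how long it may dose. A site that follows it literally stops a benefiting subject after Cycle 4. A site that follows 3.1 gives Cycle 5. The same dose is then a deviation under one section and permitted under another, and Section 6.1 rules out waivers.

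For some subjects the stop could not be reversed. Retreatment under Section 3.1 is open only to those who enter follow-up in CR, CRi or CRh and relapse after a prolonged remission. A subject stopped at Cycle 4 in MLFS, PR or stable disease has no retreatment route back to drug. What is at stake is treatment duration, exposure and consistent conduct across sites.

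**Working it through.** The plan states no figure that depends on this rule, so the check is a comparison of texts.

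**Step 1. Do the rules address the same people?**

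| Place | Who | Beyond Cycle 4? | Qualifying benefit named | Medical Monitor |
|---|---|---|---|---|
| 7.2, closing sentence | No progression, no unacceptable toxicity, benefiting | No: four cycles at most | Investigator's judgement | Not mentioned |
| Summary, 3.1 | Benefiting, no unacceptable toxicity | Yes | Any CR, MLFS, PR, stable disease | Named after stable disease; scope ambiguous |
| 6.4 | Benefiting, tolerating drug | Yes | Stable disease, PR, CR | All who continue |
| Figure 1 footnote c | Benefiting, tolerating drug | Yes | Stable disease, PR | All who continue |
| Tables 7 and 36, footnotes b and n | Those dosed beyond Cycle 4 | Yes | Not listed | All who continue (footnote n) |

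They do. The cap in 7.2 and the permission elsewhere apply to the same non-progressing, benefiting subjects, so this is not a general rule with a stated exception.

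**Step 2. Could the cap be the intended rule?** No. On-treatment visits at Cycle 6 and Cycle 12 cannot occur under a four-cycle maximum, and footnote b would have no one to apply to. The 7.2 sentence corresponds to the first half of the 6.4 rule and lacks the half on additional cycles. The likeliest explanation is an omission in 7.2.

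**Step 3. Are the lists of qualifying benefit consistent?** They are not.

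- Section 6.4 omits MLFS. It also says: "Failure to achieve a response and not meeting the criteria for progressive disease will be considered stable disease". Section 9.6.1 counts MLFS as a response in AML, so MLFS is not stable disease. Appendix C lists it separately from CR and PR. Read literally, an MLFS subject fits none of the 6.4 categories.
- Figure 1 footnote c omits both CR and MLFS.
- For HR-MDS, Section 9.6.1 counts CR, marrow CR and PR as responses. No extension rule names marrow CR, although up to 20 of the 40 evaluable subjects in each new cohort may have HR-MDS.

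**Step 4. How many subjects are affected?** This would need the number on drug and benefiting at the end of Cycle 4. The documents do not give it.

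**The case against.** The strongest reply is that the intent is plain. The Summary and 3.1 state four cycles as the base course before giving the extension, and 7.2 merely restates the base course. Section 7.2 itself cites 6.4, where the extension is found. The discontinuation reasons in Section 11.1 do not specifically list completion of four cycles. A site working from Table 36 meets the extension in its footnotes, and a careful site would ask the Medical Monitor. This stands as far as it goes: no document shows that a subject has been or would be stopped. But it does not make 7.2 correct. A stated maximum is different from silence, and the reference to 6.4 does not point to the extension.

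Three stronger readings are tempting, and the documents do not support them.

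- **That a sizeable share of responders would lose treatment.** Section 1.2.3.1 reports 1 + 1 + 2 + 4 + 3 + 2 = 13 responses, of which 1 + 0 + 0 + 2 + 1 + 1 = 5 were MLFS. A reader might infer that about 5/13 = 38% of responders are exposed to the gap in 6.4. These are response counts from Part A and the closed 3.6 mg Part B cohort. They do not show response status at the end of Cycle 4, or that any MLFS subject reached it.
- **That 6.4 means to exclude MLFS.** Under Appendix C, MLFS requires marrow blasts below 5%, whereas PR leaves 5 to 25%. Allowing PR and stable disease but not MLFS would make little sense, and 3.1 names MLFS. This is a drafting gap.
- **That the Medical Monitor requirement is contradictory.** The phrase in the Summary and 3.1 can be read as applying to stable disease alone or to every category. The second reading agrees with 6.4 and footnote n, so this is an ambiguity only.

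Nor does the number of places that allow extension measure the size of the problem, since several repeat the same sentence or footnote.

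**Conclusion.** The contradiction is real and sits in current operative text. Section 7.2 caps benefiting subjects at four cycles; the Summary, 3.1, 6.4, Figure 1 footnote c and Tables 7 and 36 do not. The section on dosing carries the wrong rule, and it should be corrected while the Days 1-7 cohorts are enrolling. The differing response lists are a secondary alignment matter, and the Medical Monitor wording is optional.

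The size in subjects is unknown. No sample size, error rate or stated figure changes. The conclusion assumes that extension beyond Cycle 4 is what the sponsor intends, which every place except 7.2 supports.

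**What to change.** 1. Replace the closing sentence of 7.2 with text to this effect: *Subjects without progressive disease (Section 6.4) or unacceptable toxicity may be treated through Cycle 4 if the Investigator judges that they benefit. Further cycles may be given, once discussed with the Medical Monitor, to subjects who tolerate the drug and have clinical benefit (AML: any CR, MLFS, PR or stable disease; HR-MDS: CR, marrow CR, PR or stable disease), until that benefit is lost.*
2. Qualify the reference to Cycles 1 to 4 in the opening sentence of 7.2 so that it does not restate the cap.
3. Use the same list of qualifying responses in 6.4 and in Figure 1 footnote c.
4. Optionally, make clear in the Summary and 3.1 that Medical Monitor discussion applies to every category, as 6.4 and footnote n already state.

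Footnotes b and n need no change, nor does the Summary's separate allowance for dosing beyond progression. The cost is a few edited sentences. No visit, sample or procedure is added, and no consultation step is removed.
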